### **Month 12 [Day 365 ± 30 days]: Telephone Contact**

The following will be performed:

- Adverse events.
- Concomitant medication.
- Premenopausal women should be reminded that they are strongly advised not to become pregnant while on study and should continue using appropriate contraceptive methods.
- Mail or email the 4-OHT Diary to the participant. Ask the participant to record their daily use of agent on the 4-OHT Diary; using a new Diary for each Canister.
- Participants will be asked to extend their gel application and will be reconsented following the CIRB remote consent procedure for the extended gel application.
- Ship or have the participant pickup a new 6-month supply of the study agent.
- Instruct the participant to keep all used canisters and to bring the canisters with all of their completed Diaries to the next in person clinic visit.
- Drug compliance and agent diary review.

- Mail or email the **BESS QUESTIONNAIRE** to the participant ahead of the telephone visit, if possible. Ask the participant to fill it out ahead of the visit, to sign and date the form at the time of completion, and keep it. Collect the information during the visit, if allowed by the institution and if the participant feels comfortable to discuss the responses over the phone. Participants should return the **BESS QUESTIONNAIRE** at their next in person visit. If you were not able to mail/email the **BESS QUESTIONNAIRE** ahead of the telephone visit, collect the information over the phone, if possible. Record the answers.
- Participants will be reminded of the need to reschedule their mammogram within the next 6 months.
- Participants that do not want to extend their gel application should be taken off agent and asked to allow the collection of their next available mammogram for study purposes.

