## 7.4 Evaluation at Completion of Study Intervention

### Month 13-18

The following will be performed:

- Physical exam, including a breast examination.
- Vital signs, weight.
- Laboratory tests will include the following:
  - CBC (hemoglobin, hematocrit, RBC, WBC, platelet count)
  - Total bilirubin
  - AST (SGOT)/ALT (SGPT)
- In women who were considered premenopausal at baseline: FSH, LH, estradiol.
- A urine or serum pregnancy test will be performed. The urine pregnancy test must be done in the clinic. If the pregnancy test result is positive at the 13-18 Month visit, follow the pregnancy to term and complete the Outcome of Pregnancy CRF. Do not take the participant off study until the completion of the pregnancy when the outcome of pregnancy is known.
- Bilateral mammogram. The raw images must be obtained (see instructions in Section 8.1) for study purposes.
- For participants who underwent the baseline breast biopsy, the biopsy will be repeated if participant extended their gel application.
- Blood draw for research biomarkers
- Adverse events.
- Concomitant medication.
- Collect unused study agent.
- Compliance check will be performed by evaluating the participant's agent diary.
- BESS Questionnaire (refer to Appendix E).
- Tobacco and Alcohol use assessment will be performed at Month 12, using the Month 12 questionnaires (see Appendix G "Alcohol and Tobacco Use Assessment Questionnaires – Month 12").
- Participants will be reminded of the need to return for their next annual mammogram (Month 24 + 8 Months), which is their standard clinical high risk follow-up visit.

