### 8.2 Secondary Endpoints

Note: data from Month 13-18 visit instead of Month 12 visit will be used if participants were seen under the COVID-19 Contingency Plan. If data were not collected at Month 6 under the COVID-19, such

participants will have missing data.

Breast biopsy for secondary and exploratory endpoints will be performed in the opposite (non-target) breast.

8.2.1 We will estimate and compare the percent change in mammographic breast density (using Volpara) from Baseline to Month 12 in women applying 2mg 4-OHT gel per breast versus placebo.

8.2.2 We will estimate and compare the percent change in mammographic breast density (using LIBRA) from Baseline to Month 12 in women applying 2mg 4-OHT gel per breast versus placebo.

8.2.3 We will compare the percentage of women who underwent a change in BIRADS category, comparing pre-and post- treatment measurements, for recipients of 4-OHT gel versus placebo.

8.2.4 We will conduct subgroup analyses including BIRAD category, menopausal status, cup size, and total breast volume.

8.2.5 We will estimate the percentage of women with  $\geq 10\%$  absolute decrease in quantitative mammographic density percentage between baseline and 12 months, comparing between treated group 2mg per breast 4-OHT gel versus placebo based on Cumulus method.

8.2.6 Markers of Toxicity: Baseline, 6 and 12 months BESS questionnaire will be used. Further blood based toxicity markers will be also evaluated at baseline and again at months 6 and 12 (F VIII, vWB factor, SHBG, lipid profile).

8.2.7 Markers of Tamoxifen exposure (in plasma): Plasma measurements of 4-OHT and related metabolite levels and factors related to tamoxifen exposures will be measured at baseline and again at months 6 and 12. (If baseline drug metabolite levels are low; other plasma biomarkers will not be measured at baseline and month 12. Further, the second analysis of 4-OHT and metabolites at 6 and 12 months will also not be performed).

8.2.8 Markers of Tamoxifen exposure (in tissue): Tissue measurements of 4-OHT and related metabolite levels and factors related to tamoxifen exposures will be measured at baseline and again at month 12. (If baseline drug metabolite levels are low; other tissue biomarkers will not be measured at baseline and month 12. Further, the second analysis of 4-OHT and metabolites at 12 months will also not be performed).

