
We will evaluate if the change of breast density is different in patients with heterogeneously dense (C) vs extremely dense (D) breast at baseline, by incorporating this covariate and its interaction with treatment over time in the repeated measures analysis.

Due to the COVID-19 closures of clinical research activities, a small number of participants (less than 20) will have their month 12 visits by telephone. These participants will continue the randomized treatments and have mammograms in the month 13-18 visits. The measurements of breast density from the month 13-18 (instead of month 12) visits will be used as the primary endpoint. We will first provide summary statistics for the breast density from the month 13-18 visits, from the month 12 visit, and then graphically explore any impact of potentially longer exposures of the treatment on the primary endpoint of mammographic breast density. If appropriate, we will incorporate the timing of the measurement as a covariate in the analysis to estimate the effect of prolonged exposure of the treatment on mammographic breast density. We will also perform a sensitivity analysis by including month 13-18 measures as primary endpoint, and by excluding month 13-18 measures to evaluate the impact of the different timing of measurements on the primary endpoint analysis. For the sample size calculation, we have factored in a 19% inevaluable rate. Based on the current estimate, even including the follow-up delayed caused by COVID-19, the inevaluable rate is still within 19%. Note that patients who were randomized but never started treatments will be replaced if the inevaluable rate is above 19%.

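### Section 13.4 treats every COVID-delayed woman as still on gel, but the contingency plan lets women stop at Month 12, so the prolonged-exposure analysis would mix on-gel and off-gel readings

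*Combined protocol and SAP*

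**What the plan says.** Section 13.4 expects that "a small number of participants (less than 20) will have their month 12 visits by telephone". It continues: "These participants will continue the randomized treatments and have mammograms in the month 13-18 visits". For scoring, "The measurements of breast density from the month 13-18 (instead of month 12) visits will be used as the primary endpoint". After summaries and graphs it adds a further step, conditional on its being judged suitable: "we will incorporate the timing of the measurement as a covariate in the analysis to estimate the effect of prolonged exposure of the treatment". The only sensitivity analysis specific to COVID runs the comparison with and without the Month 13-18 readings.

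The COVID-19 Contingency Plan in section 7 describes a second route. At the Month 12 telephone contact, women are asked to extend gel use and are reconsented. Those who decline "should be taken off agent and asked to allow the collection of their next available mammogram for study purposes". For the Month 13-18 visit, the same plan says that "the biopsy will be repeated if participant extended their gel application". It sets no such condition on the research blood draw.

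For secondary endpoints, the note in section 8.2 says that "data from Month 13-18 visit instead of Month 12 visit will be used if participants were seen under the COVID-19 Contingency Plan". Section 13.5 carries a similar note.

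**The concern.** The visit plan provides for two kinds of delayed woman and the analysis plan recognises one. Among women who extended, a mammogram at a later month follows more months of gel. Among women who stopped at Month 12, it follows the same 12 months of gel and more months without it. A single timing variable read as exposure gives both the same value. What is at stake is the meaning of the prolonged-exposure estimate and of the Month 13-18 summaries, which the plan relies on to judge whether the COVID delay affected the primary endpoint. A smaller question concerns plasma: if non-extenders give blood at Month 13-18, the substitution notes would enter an off-drug 4-OHT level as a Month 12 value.

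**Working it through.** **1. Size of the group.** Sections 13.1 and 13.4 give 158 randomized, about 19% not evaluable, and fewer than 20 delayed.

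- Evaluable women: 158 × (1 − 0.19) = 127.98, which reproduces the plan's 128.
- Delayed women, at most 19: 19/158 = 12.0% of those randomized, or 19/128 = 14.8% of those evaluable if all 19 are evaluable.
- The number k who declined extension is not given. As an assumed range, the off-gel share of a delayed group of 19 is k/19: 0% at k = 0, 26% at k = 5, 53% at k = 10, 100% at k = 19.

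**2. What the timing variable measures.** Take two women scanned at Month 16, both using gel daily until they stop.

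| | Extended | Stopped at Month 12 |
|---|---|---|
| Timing covariate (months) | 16 | 16 |
| Months of gel | 16 | 12 |
| Months off gel at scan | 0 | 16 − 12 = 4 |

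The covariate is identical and the exposure is not. Across Month 13-18, a woman who stopped at Month 12 is 1 to 6 months off gel when scanned.

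**3. Whether the planned analyses separate them.**

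- *With and without Month 13-18 readings (13.4).* This splits by date of scan. Both women above are kept together or dropped together.
- *Compliance and per-protocol analyses (13.5).* Section 5.6.1 counts a woman as compliant if she used gel for at least 9 months and on 75% of days in the interval. The woman who stopped has 12 months of use. If the interval ends with treatment, her adherence is 12/12 = 100%. If it ends at the final mammogram, it is 12/16 = 75% at Month 16 (compliant), 12/17 = 71% at Month 17 and 12/18 = 67% at Month 18. She therefore counts as compliant on the first reading of the interval, and through Month 16 on the second.
- *Longitudinal compliance covariate (13.5).* It could carry the information, but no rule says how days after a permitted stop at Month 12 are coded.

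**4. Whether off-gel women are really expected at Month 13-18.** The biopsy condition in the contingency plan has a purpose only if some women reach that visit without having extended. This is an inference, but a firm one. That they also give blood there is less certain, because the opt-out text asks them only for a mammogram.

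**5. First mammogram after Month 18.** Sections 1.1, 8.1 and 13.4 define the primary reading as Month 12 or Month 13-18. The contingency plan's next window is Month 24 + 8 months, so a first reading in Months 19-23 falls in neither. Section 13.6 makes a woman without primary data not evaluable for that endpoint, while admitting available data to the repeated-measures analysis. The answer can be inferred, but it is not written down.

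**The case against.** The best defence is that the primary analysis is unaffected. Section 13.4 compares arms as randomized regardless of compliance, and section 8.4 asks women who stop the agent to stay on study so that their mammograms can be collected. Including non-extenders is therefore stated policy. That stands. A reader might infer that the trial loses power or that the primary comparison is biased. The documents support neither: the number of non-extenders and the effect retained off gel are both unknown, and any dilution is one that the intent-to-treat policy accepts.

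The timing analysis is also hedged. It begins with summaries and graphs, speaks only of potentially longer exposure, and adds the covariate if appropriate. Section 5.6.1 acknowledges that the interval to the final mammogram may vary. This lowers the stakes, but none of it separates the two groups.

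Three further inferences go too far:

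- That longer use and time off gel push density in opposite directions. Whether a reduction persists after stopping is itself an exploratory question of this trial (section 1.3).
- That readings after Month 18 are wholly uncontrolled. The Month 12 contact includes a reminder to reschedule the mammogram within six months, and the primary reading definition together with 13.6 largely settles the matter.
- That the plasma-tissue correlation is distorted. Non-extenders have no repeat biopsy, so they contribute no post-treatment pair.

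**Conclusion.** The statement in 13.4 that all delayed women continue treatment does not agree with the contingency plan, and the prolonged-exposure analysis built on it would label some off-gel readings as longer exposure. It concerns an unknown number of women, at most 19, and a conditional, secondary use of the data; the primary intent-to-treat test and its population are not shown to be wrong. The conclusion assumes that at least one woman declined extension and supplied a mammogram in the Month 13-18 window. If none did, only the wording is at fault. The plasma part rests on the further assumption that non-extenders gave blood at that visit. The correction is worth making because it is nearly free and the result would otherwise be hard to interpret. No view is taken on whether women should extend or stop.

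**What to change.** Reconcile section 13.4 with the contingency plan, before density change is compared by arm:

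1. Name both groups in 13.4: women who extended gel and women who stopped at Month 12.
2. Keep both in the primary analysis, regardless of compliance, with the Month 12 or Month 13-18 reading.
3. Restrict the prolonged-exposure analysis to women who extended, and replace scan timing with gel duration from first to last application in the diary.
4. Show non-extenders separately in the timing summaries and in the sensitivity analysis.
5. In 8.2 and 13.5, state that plasma 4-OHT from a non-extender at Month 13-18, if drawn, is not a Month 12 on-treatment level.
6. State that a first post-baseline mammogram after Month 18 lies outside the primary reading definition and is handled under 13.6.

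The cost is a few sentences, one indicator and one derived duration. The sources already exist: reconsent records (schedule 7.1.2, Note 5), dated diaries (Appendix D) and the scan dates kept with the images (10.2). The drawback is slightly smaller sets for the exploratory exposure and plasma summaries, and a duration only as good as the diaries returned.

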### 13.5 Secondary and Exploratory Objectives, Endpoints, Analysis Plans

Note: data from Month 13-18 visit instead of Month 12 will be used if participants were seen under the COVID-19 Contingency Plan.

The secondary objectives are:

1. To estimate and compare the percent change in mammographic breast density (using Volpara) from Baseline to Month 12 in women applying 2mg 4-OHT gel per breast versus placebo.
2. To estimate and compare the percent change in mammographic breast density (using LIBRA) from Baseline to Month 12 in women applying 2mg 4-OHT gel per breast versus placebo.
3. To compare the percentage of women who underwent a change in BIRADS category, comparing pre-and post- treatment measurements, for recipients of active agent versus placebo.
4. To conduct subgroup analyses including BIRAD category, menopausal status, cup size, and total breast volume.
5. To estimate percentage of women with  $\geq 10\%$  absolute decrease in quantitative mammographic density percentage between baseline and 12 months, comparing between treated group 2mg per breast 4-OHT gel to placebo based on Cumulus method.
6. To describe symptoms assessed by BCPT Eight Symptom Scale (BESS) questionnaire and laboratory toxicity assessment (Factor VIII (F VIII), Von Willebrand (vWB) factor, Sex Hormone-Binding Globulin (SHBG), lipid profile).
7. To evaluate plasma measurements of 4-OHT and related metabolite levels and factors related to tamoxifen exposure.
8. To evaluate tissue measurements of 4-OHT and related metabolite levels and factors related to tamoxifen exposure.

The exploratory objectives are:

1. To compare the Cumulus vs. Volpara vs. LIBRA breast density measurement methods to estimate percent change in mammographic breast density from baseline to Month 12 in women applying 2mg of 4-OHT gel per breast vs. placebo.
2. To perform correlation of drug concentrations in the plasma and the tissue.
3. To evaluate plasma measurements of Insulin-like growth factor (IGF) pathway members, C-reactive protein (CRP), and estradiol.
4. To compare the 2D natural vs. 2D synthetic breast density measurement using the Cumulus method to estimate percent change in mammographic breast density from baseline to Month 12 in women applying 2mg of 4-OHT gel per breast vs. placebo.
5. To evaluate tissue biomarkers (among women undergoing optional pre- and post-treatment biopsies):  
Terminal duct lobular unit (TDLU) Involution  
Collagen structural changes  
SETER/PR index: estrogen related transcription  
Ki-67, COX-2, p16, CD68.
6. To examine whether any reductions in mammographic density seen after 1 year of 4-OHT vs. placebo gel application persist at 24 months (or longer under the COVID-19 Contingency Plan), one year after gel application has stopped.

All available data will be summarized and analyzed for the secondary analysis. At the end of the study, participant demographic characteristics; the following measurements at baseline and 52 weeks: 1) MD of the breast, 2) tissue biomarkers (among women undergoing optional pre- and post-treatment biopsies: TDLU Involution, Collagen structural changes, SET index, Ki-67, COX-2, p16, CD68, etc.), 3) plasma measurements of parent drug and related metabolite levels and factors related to 4-OHT exposures, such as IGF pathway members, CRP, estradiol, bisphenol and 4-OHT; and the percentage of women with  $\geq 10\%$  absolute decrease in percent MD between baseline and 52 weeks will be summarized using descriptive statistics, such as mean, standard deviation, median and range for continuous variables and frequency/percentage for discrete variables. The difference of continuous variables between baseline and 52 weeks may be compared between two groups using t-test or Wilcoxon rank sum test, whichever is appropriate. Multivariate analogues to the before mentioned univariate tests, such as Hotelling's  $T^2$  test and multivariate multiple regression will be employed when appropriate. Transformation may be performed when necessary to make continuous variables close to normal distribution before evaluating the change of these continuous variables over time between two groups using repeated measures analysis where the intra-participant correlation is taken into consideration, adjusting for other important covariates. In addition, longitudinal data analysis such as the linear mixed effect model will be applied to evaluate the mammogram density change over time. The treatment effect will be evaluated adjusting for other important covariates. The effect of compliance will be evaluated in the per protocol analysis.

The percentage of women with at least 10% decrease in percent change of MD will be estimated and compared between two groups using chi-squared or Fisher's exact test whichever appropriate. We will also explore the correlation between percent change in MD and other markers using Spearman correlation at baseline or by employing repeated measures analysis when both baseline and 52-week data are included and intra-participant correlation is accounted for. We will also monitor and summarize any adverse events observed in women on this study.

The change in percent MD of the breast from the end of the treatment at 1 year to 1 year after the treatment ends will also be summarized using descriptive statistics, such as mean, standard deviation, median and range for each arm. The difference of this change in percent MD will be compared between two treatment groups using t-test or Wilcoxon rank sum test, when appropriate. Multivariate methods such as simultaneous 95% confidence intervals will be used for estimation purposes when appropriate.

We will define three groups of participants by the menopausal status change during the study, pre-menopausal/pre-menopausal, pre-menopausal/post-menopausal and post-menopausal/post-menopausal, and compare the change of MD and other secondary endpoints among these three groups of participants by Kruskal-Wallis test. We may incorporate this grouping covariate in the repeated measures analysis to evaluate any differential effect of menopausal status change on the change of endpoints by treatment over time. Sensitivity analysis on the treatment effect with and without including women who undergo menopausal transition will be performed. Sensitivity analysis on the treatment effect with and without including women on hormone replacement therapy will be performed. The treatment effect will be analyzed by incorporating the longitudinally measured compliance data as a covariate.

If prior imaging is available (mammogram or other modalities), the data will be collected and summarized. Other statistical methods, such as the MANOVA and multivariate multiple regression, may be used when appropriate.

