#### Tissue Biomarkers

Overview: Tissue biomarkers have been selected to interrogate the following targets that represent:

- a) Structure-function activity of terminal ductal lobular units (TLDUs) by counting acinar density
- b) Breast tissue density by assessing the patterns of collagen matrix
- c) Hormone-mediated cellular activity by measuring the transcriptional expression levels of ER-alpha and ER-associated genes (SETER/PR index)

- d) Pharmacogenomic response to endocrine therapy by measuring Ki67 protein by immunohistochemistry and aurora kinase-alpha gene expression
- e) Inflammatory response to 4-OHT therapy by measuring COX2 and p16 proteins, and recruitment of CD68 monocytes.

All biomarkers will be compared in biopsies obtained before and after exposure to the 4-OHT gel, in order to explore pharmacodynamic responses of interest. That said, the baseline measures will also be evaluated, particularly for items a-c (above) that might be less likely to change in response to short-term exposure, but combine to provide the cellular, matrix and targeted molecular context of the tissues in each participant prior to exposure to treatment.

*a) TDLU Involution:* TDLU involution is characterized by a reduction in the number and size of TDLUs and their secretory acinar units. Reduced involution in TDLUs has been associated with increased risk of breast cancer in several studies of women with benign breast disease. Furthermore, a recent study showed that, especially amongst premenopausal women, reduced TDLU involution was associated with higher area and volumetric MD; indicating that TDLU involution and MD are correlated markers of breast cancer risk. In continuation of this, there is also data suggesting that increased MD and reduced TDLU involution are actually independent risk factors for breast cancer. Taken all these together, in our proposal, as an exploratory endpoint, our aim is to assess TDLU involution, correlate with MD and evaluate whether baseline TDLU involution correlates/predicts change in MD induced by 4-OHT gel. The TDLU density (acini per TDLU) is readily determined from pathologic review of the same routine H&E stained tissue sections that are usually used for diagnosis using image analysis tools for area-based quantitation.

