The SETER/PR index assay is technically feasible using sections from 20-gauge core biopsy samples from metastatic sites (2-3 cores), whereas many mamotome core biopsy samples of proliferative benign histologic lesions are of 11-gauge or 9-gauge and contain considerably more epithelial tissue. In our limiting dilution study using purified RNA, this assay provided accurate measurement down to 30 ng of RNA, and that is considerably less than we typically obtain from core biopsy sections. This project will be the first to evaluate the SETER/PR index in the setting of endocrine therapy in benign tissues (and is therefore innovative) so the rationale is based on the index as a measure of ER-related transcription, a biological process that is known to be important in benign breast disease, and is central to the pharmacology of the prevention strategy to be tested. We will also analyze the ratio of fatty/non-fatty tissue. Our analysis will explore two hypotheses: i) whether pharmacodynamic responses to exposure of tissues to 4-OHT (e.g. reduction in proliferation or TLDU density) will be greater when the tissues have higher SETER/PR index; and ii) whether exposure to 4-OH decreases the SETER/PR index.

d) *Markers of proliferation and inflammation*: Ki-67 has been widely evaluated in previous phase I and II prevention trials that have revealed conflicting data. In one study, a reduction in Ki-67 was seen with 6 months of letrozole therapy; whereas another study did not show any changes with 6 months of letrozole therapy. In another study of arzoxifene, no changes in Ki-67 were seen. A separate study was done in premenopausal women using 12 months of lignans and a reduction in Ki-67 was observed.

It is possible that the mechanism of action for Ki-67 reduction is different for tamoxifen and indeed a reduction in Ki-67 in patients with DCIS has been shown with oral as well as 4-OHT. However, the effect in breast tissue of high risk women is not known. Therefore, we would like to evaluate changes in Ki-67 induced by 4-OHT in our study.

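### Section 13.5 names neither arm nor a marker-by-arm term for the exploratory question of whether baseline tissue markers predict 4-OHT-induced density change

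*Combined protocol and SAP*

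**What the plan says.** **The question.** Under Tissue Biomarkers, section 2.3 sets an exploratory aim for TDLU involution: to "evaluate whether baseline TDLU involution correlates/predicts change in MD induced by 4-OHT gel". The collagen paragraphs there note that nothing is known about collagen structure as a predictor of the same change. For the SET index, section 2.3 gives a related hypothesis about tissue response: "whether pharmacodynamic responses to exposure of tissues to 4-OHT (e.g. reduction in proliferation or TLDU density) will be greater" with a higher index.

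**The method.** Section 13.5 has one sentence that relates markers to density change: "We will also explore the correlation between percent change in MD and other markers using Spearman correlation at baseline", continuing "or by employing repeated measures analysis when both baseline and 52-week data are included and intra-participant correlation is accounted for". It mentions no arm, does not say whether the arms are combined, and names no marker-by-treatment term.

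**How other modifiers are handled.** For baseline density category, section 13.4 examines whether density change differs "by incorporating this covariate and its interaction with treatment over time in the repeated measures analysis". For menopausal transition, section 13.5 leaves open a model "to evaluate any differential effect of menopausal status change on the change of endpoints by treatment over time". The tissue and plasma markers get neither. Section 13.5 does compare marker changes between arms, but that tests whether the gel moves the marker, not whether the baseline marker predicts the gel's effect on density.

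**Plasma and tissue drug levels.** Exploratory objective 2 reads "To perform correlation of drug concentrations in the plasma and the tissue", with no population stated.

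**The concern.** Whether a baseline marker predicts drug-induced change is a question of effect modification: does the difference between gel and placebo vary with the marker? A marker–change correlation taken across both arms answers something else, namely whether women with a high marker lose more density whatever they received.

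The distinction matters here. The sample size section assumes a 2% fall on placebo, and section 2.3 describes density as falling with age and TDLU involution as related to density. A marker of natural decline is therefore plausible. If the analyst followed section 13.5 across both arms, such a marker could be taken for a predictor of response to 4-OHT. A marker that predicts only on gel would have its correlation diluted by the placebo women.

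**Working it through.** **1. The plan's own figure.** Section 13.1 gives a 6% versus 2% decrease, SD 8%, two-sided 0.05 and 80% power. The standardised difference is (6 − 2)/8 = 0.5. A two-sample t-test needs 63.8, so 64 per arm, with power 0.801 at 64. Attrition is 1 − 128/158 = 19.0%. The design figures reproduce. No figure is given for the marker analysis.

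**2. Inputs for the marker check.** From section 13.1: mean changes of −2 and −6, SD 8 in each arm, and 64 evaluable per arm. Assumed, because the documents give no value: the marker–change correlation r (0.2, 0.3, 0.4 in size) and 20 biopsied women per arm. Biopsy is optional and no number is stated.

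**3. What a cross-arm correlation picks up.** The mean difference of 4 raises the combined SD to √(8² + 2²) = 8.25. A purely prognostic marker, with the same r in both arms, has a combined Pearson correlation of 8r/8.25 = 0.97r, so almost all of it survives. A marker that predicts only on gel (0.4 on gel, 0 on placebo) has (0.4 × 8)/2 ÷ 8.25 = 0.19, about half its gel-arm value.

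**4. Simulation.** Percentage of trials significant at two-sided 0.05. There were 4,000 simulated trials per scenario; a repeat of the listed scenarios with 6,000 moved no figure by more than about 2 points.

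| Per arm | r placebo / gel | Spearman, both arms | Spearman, gel arm only | Marker-by-arm test |
|---|---|---|---|---|
| 64 | 0.2 / 0.2 | 54–55 | 32 | about 5 |
| 64 | 0.3 / 0.3 | 90 | 64 | about 5 |
| 64 | 0.4 / 0.4 | 99 | 88 | about 5 |
| 64 | 0 / 0.4 | 56 | 88 | 62–63 |
| 20 | 0.2 / 0.2 | 20 | 12 | about 5 |
| 20 | 0.3 / 0.3 | 41 | 22–24 | about 5 |
| 20 | 0.4 / 0.4 | 66 | 38 | about 5 |
| 20 | 0 / 0.4 | 20–22 | 37–39 | 22–23 |

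Where r is equal in both arms the marker has no predictive value, and only the interaction test says so. Restricting the correlation to the gel arm does not help, because it too responds to a prognostic marker.

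**5. Hand check of interaction power.** The slope difference is 0.4 × 8 = 3.2. Its variance is about (64 + 64 × 0.84)/n = 117.8/n. At n = 64 the SE is 1.36 and the ratio 2.36, giving roughly 66% power. At n = 20 the SE is 2.43 and the ratio 1.32, giving roughly 26%. These large-sample values sit slightly above the simulated ones, as expected.

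**6. Plasma–tissue correlation, extreme case.** Suppose half the women are tied at zero on both measures and the gel-arm values are independent. On a 0–1 rank scale the arm means are 0.25 and 0.75, so the covariance is 0.0625. The variance is 0.0625 + ½ × 0.25/12 = 0.0729. The rank correlation is 0.0625/0.0729 = 0.86, with no relationship within the gel arm.

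**The case against.** A reader might infer that the plan ignores arm, that Spearman is its only method, and that prognostic markers will be reported as predictors of response. The documents do not support any of these. Pooling is an inference from silence. The same sentence offers repeated measures, and elsewhere the plan describes repeated measures with treatment in the model. The sentence promises only to explore a correlation. Change in density does not exist at baseline, so the Spearman step may simply mean a cross-sectional marker–density correlation before treatment, for which combining the arms is proper. All this stands. What remains is that neither route, as written, names the term that answers the question in section 2.3.

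The predictive wording is also background text, labelled exploratory; the numbered objective only evaluates tissue biomarkers. The SET hypothesis concerns tissue response rather than mammographic density, so the density sentence is not its stated method. Both points stand and limit the weight of the matter.

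The percentages depend on assumed r and an assumed biopsy count, and the simulated correlations are real associations. They become errors only if called predictive. That is correct.

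The interaction test would miss most truly predictive markers at 20 per arm. This must be stated, but it does not favour the cross-arm correlation, which does no better for the same marker (20–22% against 22–23% at 20 per arm; 56% against 62–63% at 64).

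On drug levels, the 0.86 needs placebo values tied exactly at zero. It falls to 0.75 with independent assay noise and disappears if undetectable values are excluded. Analysts would probably handle this sensibly, so it is a clarification only.

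**Conclusion.** The point holds as a gap in specification. Section 2.3 poses a predictive question about baseline tissue markers, and section 13.5 specifies neither arm nor a marker-by-arm term for it, although section 13.4 does so for baseline density category.

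The size is conditional. If the correlation were taken across both arms, a purely prognostic marker would be significant in about 20–66% of trials at 20 per arm and 55–99% at 64, against about 5% for the interaction. This rests on an assumed r of 0.2 to 0.4, equal in both arms. With optional biopsies, 64 per arm is an upper bound that tissue markers are unlikely to reach.

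It would go too far to say that the plan pools the arms or will mislabel markers; it leaves the choice open. The issue is exploratory, and the fix is worth making because it is cheap.

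**What to change.** In section 13.5:

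- For the exploratory predictor questions, model Month 12 density change (Month 13–18 under the COVID-19 plan) on arm, baseline marker and marker-by-arm. Report the interaction estimate with its 95% confidence interval.
- Show marker–change correlations by arm as descriptive only, and say that a gel-arm correlation alone does not separate prognostic from predictive.
- State that interaction power is low (about 22–23% at 20 per arm and 62–63% at 64, for r = 0.4 on gel and 0 on placebo) and that results are hypothesis-generating.
- As a minor clarification, state that exploratory objective 2 uses 4-OHT arm samples.

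The cost is a few lines of text. No new data, visits or participants are needed. The price is a wide interval for the interaction, which reflects what the biopsy subset can support.
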